5.1.6 Left Atrial Appendage (LAA) Exclusion

The left atrial appendage should be managed using the AtriClip PRO (PRO1 or PRO2) device. Only if the surgeon deems that the AtriClip Pro device is not able to be utilized for Left Atrial Appendage exclusion because of anatomical limitations, the surgeon may utilize a stapling device in accordance with surgical standard of care (SOC). If the surgeon determines it is not feasible or safe to address the LAA, the appendage may be left intact.

General Placement of the AtriClip PRO:

The PRO1 is introduced into the chest through the incision (the PRO2 fits through a trocar) at the 6th or 7th intercostal space directing it toward the base of the Left Atrial Appendage. Using soft endoscopic forceps or a Kitner in the surgeon’s right hand, the open AtriClip device is passed over the tip of the left atrial appendage. The tip of the appendage is gently teased into the AtriClip. The device is then lowered into the base of the appendage. The skillful manipulation of the endoscope will allow the surgeon to see all angles and visualization surrounding structures and assess whether the appendage is fully contained within the AtriClip. Awareness of the proximity of the circumflex artery and its relationship to the targeted location at the base of the left atrial appendage is critical. Using the transesophageal echo (TEE) to help guide placement, the AtriClip is applied on the left atrial appendage ensuring the alignment and complete closure of the LAA. Refer to the IFU for proper AtriClip size selection.

AtriClip Deployment at Base of LAA

When the surgeon is satisfied with the AtriClip position, the surgeon releases the activation lever on the device, allowing the AtriClip to close upon the appendage. At this point, it is important to identify the subject's QRS electrograms to ensure that there are no QRS changes, and no coronary vessels have been occluded. Transesophageal echo (TEE) is examined to ensure that the entire appendage is included within the AtriClip and there is no blood flow to the appendage. A TEE with Doppler will be performed to verify exclusion of the LAA and assess for any residual pouch and also evaluate the base of the LAA along the entire length and depth of the excluded appendage. If not completely excluded, the AtriClip is re-opened and re-deployed. When the AtriClip is satisfactorily positioned around the base of the appendage, the deployment tab is pulled on the applier to fully deploy the AtriClip to the base of the left atrial appendage.

Once deployed, carefully squeeze the activation lever to retract the pull bar against the loop. Providing counter pressure on the AtriClip per the surgeon's discretion, carefully remove the applier deployment loop from the LAA, leaving the AtriClip undisturbed. Gently remove the AtriClip applier device from the thoracic cavity.

After placing the AtriClip LAA Exclusion Device on the Left Atrial Appendage and removing the deployment tool, the surgeon will place the Isolator Pen (MAX5) near the Apex of the LAA. The ASU/ASB dial will be set to PSS on the O.R. lab and the Pen will sense for atrial electrograms. The surgeon will then ask the O.R. lab operator to initiate pacing while the pen is in contact with the Apex of the LAA if the patient is in sinus rhythm. Pacing should be performed at 20 BPM above the intrinsic rate. Electrical isolation of the LAA from the Left Atrium is confirmed if there are no atrial electrograms present during sensing from the LAA or there is no capture during pacing, i.e., the heart rate stays constant and does not equal the pacing rate.

Surgical Stapler Method

The surgeon should introduce a stapling device and carefully position it around the base of the LAA. Using the transesophageal echo (TEE) to help guide placement, the stapler is closed on the base of the atrial appendage and it is amputated. The amputated LAA is withdrawn from the stapler. A TEE should be performed to evaluate the base of the LAA along the entire length and depth of the excluded appendage. If it is determined that exclusion is not complete (i.e., there is blood flow between the LAA and the LA at any point), additional thoracoscopic methods such as sutures or clips may be used to exclude the LAA completely.

Closure & Epicardial Procedure Completion

The pericardium may be re-approximated with a single suture using a laparoscopic suturing device such as the commercially available Endo Stitch™ device. If closure of the pericardium seems to be putting any tension on the deployed AtriClip, this step is not performed. A chest tube is placed, the lung inflated and visualized. The ports are then withdrawn. The subject should be ventilating both lungs effectively. Sterile dressings are applied.

Restoration of Sinus Rhythm

If the subject is not in sinus rhythm at the end of the epicardial surgical procedure, electrical cardioversion may be performed, at the discretion of the surgeon, understanding that these subjects are not typically anticoagulated at this time. The subject is then transferred to the post-operative care ward.

Post Epicardial Surgical Procedure - Subject Assessment

To assess the subject status with regard to potential bleeding, assessments of hemoglobin and

hematocrit shall be performed post-surgical ablation procedure.

Esophagoscopy

An esophagoscopy must be conducted and/or obtained **between 24-72 hours** following the Epicardial Surgical Ablation Procedure. (Refer to Protocol Section 7.0 Subject Visit 3 for details.)

5.1.7 Post Epicardial Surgical Ablation Procedure - Antithrombotic Therapy

To protect subjects from bleeding or thromboembolic events, a suggested process for antithrombotic therapy is provided as outlined below. Investigators may utilize their institutional procedures for anticoagulation/antiplatelet therapy, in recognition of various oral anticoagulants available as well as individual subject factors such as CHADS₂ or CHA₂DS₂VAS_c score.

Within 24 Hours Post Epicardial Surgery Procedure

Within 24 hours after the surgical procedure, it is recommended that a heparin drip be restarted based on subject tolerance. When appropriate, heparin should be reduced and replaced with oral anticoagulant therapy in accordance with institutional SOC. The use of enoxaparin sodium (Lovenox) is not permitted.

Longer Term Follow-Up Post Epicardial Surgery Procedure

Oral anticoagulant therapy with warfarin (Coumadin) or another oral anticoagulant agents (NOACs) are recommended for all subjects until the Endocardial EP Ablation Procedure.

Note: If the subject does not undergo the subsequent Endocardial EP ablation procedure, per the HRS AF expert consensus statement

- Discontinuation of oral anticoagulant therapy (e.g., warfarin) post ablation is generally not recommended in subjects who have a CHA₂DS or CHA₂DS₂VAS_c score of ≥ 2 .
- The decision regarding the use of oral anticoagulant therapy (e.g., warfarin) for longer than two (2) months following ablation should be made by the physician, based on the subject's risk factors for stroke and not on the presence or type of AF.

To monitor anticoagulation for subjects on the following anticoagulation therapy, the following laboratory tests are recommended and should be measured at each follow up visit according to institutional SOC. Any additional anticoagulation testing may be performed according to institutional SOC or the physician's discretion.

- warfarin (Coumadin) - International Normalized Ratio (INR)
- dabigatran (Pradaxa) - when necessary utilize aPTT or ECT to assess for anticoagulant activity.
- apixaban (Eliquis) - no need to monitor anticoagulation effect, in cases of suspected non-compliance, or in other unusual circumstances, assessment of the anticoagulant effect of apixaban may be appropriate. The Chromogenic anti-Factor Xa chromogenic assays are preferable to the PT test because they yield more accurate results but may be used in emergency situations when an anti-Factor Xa assay is not available.
- Rivaroxaban (Xarelto) - routine measurement of Rivaroxaban plasma levels or its pharmacodynamics effects is not required or recommended. The Chromogenic anti-Factor Xa chromogenic assays are preferable to the PT test because they yield more accurate results but, may be used in emergency situations when an anti-Factor Xa assay

is not available.

5.1.8 Post Epicardial Surgical Procedure - Antiarrhythmic Medication Therapy

Subjects may be placed on a Class I or III AAD from the time following the surgical ablation procedure through the time of their Endocardial EP Ablation Procedure utilizing institutional practices, understanding that a washout period should be utilized for each medication, as appropriate. Amiodarone may be used immediately following the surgical procedure (up to one (1) day post procedure).

5.2 1st Blanking Period - Epicardial Surgical Ablation Procedure through Endocardial EP Ablation Procedure

Atrial Flutter and Atrial Tachycardia during First Blanking Period

Subjects that are in atrial fibrillation following the surgical procedure are to be treated with medication therapy prior to their EP procedure. Subjects will only be treated with a catheter ablation within the 90 Day blanking period if the subject has a non-manageable atrial tachycardia. At this time, the subject will receive the full Endocardial EP Ablation Procedure. The timing of this procedure will facilitate a new visit window timeline for the subject. **Please contact AtriCure to receive a new visit window timeline.** This will be documented in the eCRF.

5.3 Endocardial EP Ablation Procedure

All subjects should return between Day 91 – Day 121 to have the Endocardial EP Ablation Procedure performed by the Electrophysiologist. Standard cardiac electrophysiologic techniques will be used for mapping, ablation, and arrhythmia induction.

RF based, irrigated, power controlled, ablation catheters for endocardial lesions must be used for endocardial left sided catheter ablation; no other device should be used for ablation purposes in the left atrium. During ablation, it is recommended that power not exceed 50 watts and 35 watts, if the catheter is perpendicular to the tissue. Refer to the relevant Instructions for Use for further details.

The use of phased array intracardiac ultrasound (ICE) during the procedure is encouraged to guide the transeptal puncture and catheter ablation process.

Note: Transesophageal echocardiography (TEE) is used during the Endocardial EP Ablation Procedure. The transesophageal echocardiography probes should be retracted from the area of ablation prior to energy delivery as a measure to protect the esophagus and other surrounding tissue structures.

Note: The order of the below EP procedure (e.g., right-to-left or left-to-right) may be performed according to institutional practices. However, the electrophysiologist should bear in mind the following:

- Monitoring for cavo-tricuspid isthmus lesion and mitral isthmus lesion re-conduction after 20 minutes or longer following initial lesion creation is required.*
- Heparin shall be administered to maintain an ACT of > 300 seconds prior to any left atrial catheter-based ablation maneuvers.*

Note: electroanatomic mapping is required using Multipolar catheters (e.g., Lasso System)

5.3.1 Pre-Endocardial EP Ablation Procedure

Each subject should return between Day 91 – Day 121 to have the Endocardial EP Ablation Procedure performed by an Electrophysiologist.

Pre-Endocardial EP Ablation Procedure Subject Assessment

Pre-procedure data must be collected prior to starting the EP ablation procedure. See **Visit 5** for a detailed description of data to be collected.

Pre-Endocardial EP Ablation Procedure Proton-Pump Inhibitor (PPI) Therapy

It is required that an acid reducing agent be prescribed 7-days prior to the procedure and continued for a minimum of 30-days post procedure.

Patient Review

Review will be conducted with patient regarding AEF warning signs and treatment with review of the patient emergency wallet card and patient educational brochure.

Pre-Endocardial EP Ablation Procedure Antiarrhythmic Medications

If subject was placed on an AAD following the surgical procedure, it is recommended that the AAD should be discontinued for at least five (5) days (or 5 half-lives) prior to performing the EP catheter procedure to allow adequate drug washout (amiodarone should be discontinued 45 days prior to the Endocardial EP Ablation Procedure).

Pre-Endocardial EP Ablation Procedure Antithrombotic Medications

To protect subjects from bleeding or thromboembolic events, investigators may utilize their institutional procedures for anticoagulation/antiplatelet therapy, in recognition of various oral anticoagulants available as well as individual subject factors such as CHADS₂ or CHA₂DS₂VASc score.

Subjects may undergo their Endocardial EP Ablation Procedure on therapeutic levels of their oral anticoagulant (e.g., INR 2.0 - 2.5 for warfarin held for 12-24 hours prior to the procedure or based on institutional SOC) in order to protect against thromboembolic events.

5.3.2 Subject Preparation for Endocardial EP Ablation Procedure

The subject is brought to the Electrophysiology (EP) Laboratory. Either conscious sedation or general anesthesia may be used, per institutional SOC. The subject is prepped and draped according to institutional SOC, to allow access to femoral, jugular, and /or other access sites as needed.

Measures to Protect the Esophagus and Phrenic Nerve Structures during the Endocardial EP Ablation Procedure

During the endocardial procedure, standard institutional techniques should be utilized to mitigate, to the extent possible, any potential collateral injury to the esophagus and phrenic nerve structures as a result of ablation. These techniques may include, but are not limited to, the following:

- Use of intracardiac ultrasound (ICE) or transesophageal echocardiography (TEE) to guide the catheter ablation process. Note: Transesophageal echocardiography probes should be retracted from the area of ablation prior to energy delivery as a measure to protect the esophagus and other surrounding tissue structures.
- Use of an esophageal temperature probe, positioned under fluoroscopy such that it is as close to the tip of the ablation area as possible.
- Register Baseline CT/MR image with electroanatomic mapping system, to define anatomic structures.
- Phrenic Nerve Mapping. Prior to energy delivery near the ostium of the right superior pulmonary vein, SVC, or roof of LAA, perform pacing to identify phrenic nerve location relative to planned ablation site(s).
 - Pacing at high output (e.g., 10 mA) is recommended.
 - If a 3-dimensional electroanatomic mapping system is used, sites where diaphragmatic pacing is documented should be noted on the map.

Catheter Conduction Block Assessment & Ablation Steps

The following checklist of the arrhythmia assessment and catheter ablation steps to be performed by the Electrophysiologist is provided below:

Diagnostic Endocardial EP Ablation Procedure Placement

Insert multi polar Coronary Sinus (CS) catheter into coronary sinus for standard EP mapping and ablation techniques. Also, a multi electrode diagnostic HIS catheter may be placed in position for help in guidance of CS cannulation and transeptal puncture at physician's discretion.

Cavo-tricuspid Isthmus Lesion (CTI)

If subject has undergone prior catheter ablation for atrial fibrillation or Atrial Flutter, this lesion line may have been created at the time of previous ablation. In this instance, the EP should check for bidirectional cavo-tricuspid isthmus block, and, if required, perform additional cavo-tricuspid isthmus ablation.

The cavo-tricuspid isthmus lesions are created according to standard institutional practices. Check for bidirectional cavo-tricuspid isthmus block should be performed on all subjects and re-checked after a standard waiting period of 20 minutes.

Check Conduction Block of Epicardial Surgical Lesions

Using a circular mapping catheter, check for both right and left pulmonary veins isolation for entrance and exit block. Check the Posterior Box for entrance and exit block. This is typically performed using the ablation catheter; however, this may also be achieved utilizing a voltage map with a 3-D mapping system.

Gap Closure

Note: If block has not been achieved, it is required for the electrophysiologist to deliver additional ablations to the targeted site in an effort to achieve block (i.e., "gap closure"). If additional energy delivery is performed, the lesion must be rechecked for block.

If an atrial arrhythmia is present/induced during conduction block testing, then it should be mapped and ablated. If atrial fibrillation (AF) is induced, then complex fractionated atrial electrogram (CFAE) mapping and ablation may be performed.

Note: limit of 2 hours for total CFAE mapping and ablation per Endocardial EP Ablation Procedure and no more than 30cc of saline per minute with a maximum of 4 liters of saline administered for the entire Endocardial EP Ablation procedure.

Mitral Isthmus Lesion

Note: If the subject presents to the Endocardial EP Ablation Procedure in mitral isthmus dependent Atrial Flutter (“Peri-Mitral Flutter”), the mitral isthmus line must be completed by the Electrophysiologist.

The literature suggests that this will be necessary in only 15-20% of subjects.

Note: Proof of block in the box and bilateral pulmonary vein isolation should be assessed before any mitral line is initiated.

The mitral isthmus line will be initiated by the electrophysiologist from an endocardial access at the time of the Endocardial EP Ablation Procedure only if the subject presents with mitral isthmus dependent atrial flutter at the time of the EP procedure.

The maneuver will be facilitated by crossing the interatrial septum and placing an ablation catheter at the mitral valve annulus and withdrawing to the left inferior pulmonary vein isolation (PVI) line or the inferior floor line, completing the mitral isthmus line. Lesions in the coronary sinus may be needed to complete this lesion.

(Note: If the EP is unable to complete the Mitral isthmus line from this posterior approach, the EP may utilize a more anterior approach. The Mitral Line will be performed entirely by the electrophysiologist during the Endocardial EP Ablation Procedure).

Re-check Conduction Block of Mitral Isthmus Lesions

Re-check bidirectional block of Mitral Isthmus Lesion should be assessed after 20 minutes following completed ablation.

Definition of Conduction Block

For this study, endocardial entrance and exit block via pacing maneuvers will be used to assess pulmonary vein isolation and left atrium posterior wall isolation. Pulmonary vein isolation/block will be defined as pulmonary veins showing endocardial entrance and exit block with either a lasso (circling mapping catheter) or other multipolar catheters. Endocardial bidirectional block via pacing maneuvers will be used to assess the cavo-tricuspid isthmus and mitral isthmus lesions. Particular attention should be paid to block across the mitral isthmus line.

Note: It is only possible to demonstrate bidirectional (i.e., entrance and exit) block in a subject in sinus or other paceable rhythm. If the subject is in atrial fibrillation, they will not be able to be paced and only entrance block will be used to demonstrate conduction block. Utilization of local capture should be the goal, understanding that this may not always be demonstrated.

Isoproterenol or Adenosine Testing (Optional)

Per investigator discretion, once confirmation of block, or following mapping and ablation of atrial flutter or CFAEs to address AF, isoproterenol or adenosine may be administered based on institutional practices.

Complex Fractionated Atrial Electrogram (CFAE) Ablation

Complex fractionated atrial electrogram (CFAE) mapping and ablation may be performed if atrial fibrillation is induced following completion of the lesion set.

Note: limit of 2 hours for total CFAE mapping and ablation per Endocardial EP Ablation Procedure and more than 30cc of saline per minute with a maximum of 4 liters of saline administered for the entire Endocardial EP Ablation procedure.

For purposes of this protocol, complex fractionated atrial electrograms are defined as:

- (1) atrial electrograms with two or more deflections with fractionated baseline complexes, with continuous activity over a 10-second recording time; or
- (2) atrial electrograms with a cycle length \leq 120 ms over a 10-second recording time^{16, 17}.

The ablation catheter must be in stable position when recording these electrograms. A visual inspection approach (i.e., a standard EP recording system with the ablation catheter in stable position for 10 seconds to record the CFAE and capture the raw data from the procedure) will be used^{18 19}

Note: For purposes of this study, representative intracardiac electrograms at each target CFAE site should be recorded (both pre- and post-ablation).

Note: Investigational sites should review annotated pre-ablation electrogram recordings of ablated CFAE(s) to confirm whether the local CFAE met the protocol-definition of CFAEs (as defined above). This activity may be performed following completion of the EP procedure, given the potential to unduly extend procedure time as a result of performing this analysis during the procedure.

Identified local CFAE(s) may be ablated using the RF based, irrigated, power controlled, ablation catheters for endocardial lesions. During ablation, it is recommended that power not exceed 50 watts and 35 watts if the catheter is perpendicular to the tissue. Refer to the relevant Instructions for Use for further details.

The objectives for CFAE ablation are as follows:

- Technical criterion: Eliminate local CFAE (i.e., post-ablation CFAE electrogram recording is abolished as compared to pre-ablation CFAE electrogram recording).
- Procedural criterion: Termination of atrial fibrillation to either organized atrial tachycardia or sinus rhythm. If local CFAE(s) are eliminated, but the arrhythmia continues as organized atrial flutter or atrial tachycardia, the atrial arrhythmia should be mapped and ablated, with the ultimate goal of attaining sinus rhythm. Complex fractionated atrial electrogram (CFAE) mapping and ablation may be performed and stopped upon conversion to sinus rhythm (confirmed by isoproterenol testing). Alternatively, if sinus rhythm is not obtained, cardioversion is acceptable to convert the subject to sinus rhythm.

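### Protocol section 5.3.2 states the CFAE saline rate twice with opposite meaning: at most 30 cc per minute in one note, more than 30 cc per minute in the other

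*Protocol*

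**What the plan says.** Section 5.3.2 of the protocol covers the conduct of the endocardial procedure and sets limits on CFAE work in two places.

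- **Gap Closure**, in the note on what may be done if AF is induced during conduction block testing: "limit of 2 hours for total CFAE mapping and ablation per Endocardial EP Ablation Procedure and no more than 30cc" of saline per minute.
- **Complex Fractionated Atrial Electrogram (CFAE) Ablation**, in the note on CFAE work after completion of the lesion set: the same 2-hour limit, "and more than 30cc of saline per minute with a maximum of 4 liters of saline".

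Both notes close with the same cap on volume: "with a maximum of 4 liters of saline administered for the entire Endocardial EP Ablation procedure". Text on the mitral isthmus line, conduction block and optional drug testing lies between them. No other section of the protocol or SAP gives a saline rate.

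**The concern.** The two notes govern the same activity in the same procedure and give mutually exclusive rate conditions. One sets an upper limit on saline per minute. The other, read literally, sets a lower limit and gives no upper limit on the rate. An electrophysiologist cannot comply with both.

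Two things are at stake.

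- **Safety.** Among the heart-failure and ejection-fraction criteria in section 4.2.4, only NYHA Class IV and an ejection fraction below 30% exclude a patient, so NYHA Class III is not barred. Appendix 4 lists congestive heart failure and pulmonary edema among the possible adverse events, and the Appendix 5 definition of congestive heart failure names fluid overload as a possible contributor. The section headed CFAE Ablation is also where an operator would naturally look for the CFAE rules, and it carries the wording without an upper rate.
- **Deviation classification.** Section 8.2.2 defines a deviation as conduct that does not comply with the protocol. As written, every saline rate complies with one note and breaches the other, so monitors have no consistent basis for classifying it.

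**Working it through.** The plan gives no derived figure to reproduce. The check is a comparison of the two notes, followed by arithmetic on their own numbers.

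**Side by side**

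| Element | Gap Closure note | CFAE Ablation note |
|---|---|---|
| CFAE time limit | 2 hours | 2 hours |
| Saline rate r (cc/min) | r ≤ 30 | r > 30 |
| Total saline, whole endocardial procedure | 4 L maximum | 4 L maximum |

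The conditions r ≤ 30 and r > 30 have no value in common. The other two rows agree.

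**Arithmetic.** The inputs are 30 cc/min, 120 min and 4,000 cc, all from these notes. I assume continuous flow at a constant rate for the whole CFAE period. The protocol does not say this, and shorter or intermittent flow uses less.

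1. Volume at the stated rate over the full CFAE time: 30 × 120 = 3,600 cc.
2. Remainder of the cap for the rest of the procedure: 4,000 − 3,600 = 400 cc.
3. Time to reach the cap at the stated rate: 4,000 / 30 = 133.3 min, just beyond the 2-hour limit.
4. Rate that reaches the cap at exactly 2 hours: 4,000 / 120 = 33.3 cc/min.
5. Two illustrative rates above 30 (my assumption, not from the documents):
   - 35 cc/min: 35 × 120 = 4,200 cc; cap reached at 4,000 / 35 = 114 min.
   - 40 cc/min: 40 × 120 = 4,800 cc; cap reached at 4,000 / 40 = 100 min.

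**Reading the results.** Under the Gap Closure wording, a full 2 hours uses at most 3.6 L and leaves at least 0.4 L for gap closure and the isthmus lines. Under the CFAE Ablation wording, a full 2 hours uses more than 3.6 L and leaves less than 0.4 L. A sustained rate would then fit both the 2-hour period and the cap only between 30 and 33.3 cc/min; anything faster reaches the cap first.

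**The case against.** The strongest reply is that this is a dropped word with little practical reach.

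- **Drafting slip.** The second note opens with a time limit and closes with a maximum, so the rate clause sits between two upper bounds in a note otherwise identical to the first. A lost word is a plausible cause. That explains the text but does not correct it, and sites should not have to infer the direction of a fluid instruction. Loss in reading the PDF cannot be wholly excluded, but the sentence is continuous prose with no sign of a gap.
- **Total volume is still bounded.** This stands. The 4-liter cap and the 2-hour limit agree in both notes, so the contradiction is confined to the rate.
- **The 3.6 L figure does not by itself separate the readings.** This is fair: 30 cc/min is a rate the first note permits. What separates them is whether 3.6 L is an upper or a lower bound for a full 2 hours, and the 33.3 cc/min threshold.
- **Instructions for use.** Sections 1.0 and 6.0 require the catheter to be used for CFAE ablation as its instructions describe, and sections 5.3 and 5.3.2 also refer to them. Their content is not reproduced, so whether they settle the rate cannot be judged here, and the protocol's own conflict would remain.
- **Limited reach.** CFAE ablation is optional and depends on AF being induced, and the Visit 5 data list in section 7.7 names no saline-rate item. Both points are right. They limit how often the conflict arises but do not resolve it when it does.

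**Conclusion.** The concern holds. Section 5.3.2 contains two operative notes with incompatible saline rates, and nothing else in the protocol or SAP resolves them. The contradiction itself rests on the wording alone.

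Its size depends on the assumption of continuous flow over the full 2-hour CFAE period: at most 3.6 L under one wording, more than 3.6 L under the other, against a common 4 L cap. There is no effect on endpoints, analysis populations, power or type I error.

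It should be corrected because it is a fluid instruction that sites act on, in a population where NYHA Class III is not excluded. This review takes no position on which rate is right.

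**What to change.** Reconcile the notes under Gap Closure and CFAE Ablation in section 5.3.2 so that they carry one identical statement of the saline rate. Better still, state it once and cross-refer. The clinical leads should confirm the wording against the instructions for use of the permitted left atrial catheters. Notify sites of the corrected text, and tell monitors which statement applies when they classify deviations.

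The cost is a one-line protocol correction and a site memo. No change to the SAP or the sample size is needed.
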